1.1 Background

Heart failure (HF) is a public health issue around the world including China. In China, the prevalence of HF is estimated approximately 1.3% among Chinese between 35-74 years old. HF imposes a significant economic burden and poor quality of life of patient. Sudden cardiac death is responsible for half of all heart disease deaths. In Europe, the incidence of sudden cardiac death is estimated between 350,000 and 700,000 people annually (Lippert et al 2010). The estimated sudden cardiac death cases in China was 544000 deaths in 1.3 billion people every year (Hua et al 2009).

Angiotensin-converting enzyme inhibitor (ACEI) and angiotensin receptor blockers (ARB) antagonize the action of angiotensin II, a known precursor of interstitial fibrosis that is associated with ventricular arrhythmia (VA). ACEI has been used in patients with HF with reduced ejection fraction (HFrEF) over the past 2 decades. However, despites advances in pharmacological and device therapies, 50% of HF patients die within 4 years and 40% of HF patients admitted to hospital die or are readmitted within a year (ESC Guidelines 2008).

Sacubitril/valsartan is an angiotensin receptor neprilysin inhibitor (ARNI) that providing concomitant neprilysin (neutral endopeptidase 24.11, NEP) inhibition and angiotensin II type 1 (AT₁) receptor blockade. Sacubitril is a neprilysin inhibitor that inhibits the degradation of natriuretic peptides. Valsartan is an angiotensin receptor blocker that mediates the deleterious effects of angiotensin II on the cardiovascular system. Neprilysin is a ubiquitous metallopeptidase with several different substrates that cleaves vasoactive peptides with vasodilation effects (including natriuretic peptides, adrenomedullin, bradykinin, and peptides with vasoconstrictor effects). As a result of neprilysin inhibition, there are an increase of natriuretic peptides in the circulating levels, which then leads to a cardioprotective effect that counteract the detrimental effects of renin-angiotensin system and sympathetic nervous system activation (Huber and Brown 2016).

There are multiple mechanisms that may be implicated in sudden cardiac death in HFrEF patients including VA, asystole, electromechanical dissociation and cardiogenic shock. Sarrias and Bayes-Genis (2018) proposed a mechanism whereby ARNI exerts anti-arrhythmic effects by reducing myocardial cell death, hypertrophy, fibrosis and inflammation through reducing the substrates required for VA. Increase of enkephalins, endorphins, and bradykinin may also play a role in the cardioprotective and anti-arrhythmic effects of neprilysin inhibitors. However, the precise mechanism still remains unknown (Sarrias and Bayes-Genis 2018).

Results of the completed pivotal study, "The prospective Comparison of Angiotensin Receptor-Neprilysin Inhibitor with an Angiotensin-Converting Enzyme Inhibitor to Determine Impact on Global Mortality and Morbidity in Heart Failure (PARADIGM-HF) trial" found that ARNI was superior compared to ACEI in reducing the risks of death in HFrEF patients and reduce the risk of sudden death (McMurray et al 2014). In PARADIGM-HF trial, there are fewer patients' experiences serious adverse events (SAE) on ARNI than on ACEI, and fewer patients who received ARNI discontinued study due to adverse events (AE) compared to those patients who received ACEI. Hypotension was more frequently reported in ARNI patients than ACEI patients. Hyperkalemia, cough and renal dysfunction were more commonly reported in ACEI patients than ARNI patients.

Both implantable cardioverter defibrillator (ICD) and cardiac resynchronization therapy-defibrillator (CRT-D) are device-based therapies prescribed for HF patients who are diagnosed with arrhythmia or have an increased risk for arrhythmia-related sudden death. The ESC guidelines on cardiac pacing and CRT recommend prophylactic ICD or CRT in HF patients with an ejection fraction ≤35% (ESC Guidelines 2013). In 2013, approximately 2 ICD or CRT-D implantation cases were found among every million people in 2013 in China (National Center for Cardiovascular Diseases 2014). The placement of ICD and ICD-CRT improves survival and reduces sudden death rates in appropriately selected HFrEF patients (Moss et al 2009).

A previous study shown that ARNI significantly decreased sustained ventricular tachycardia (SVT), non-sustained ventricular tachycardia (NSVT), and premature ventricular contraction (PVC) in 120 patients with ICD or CRT-D (de Diego et al 2018). Nevertheless, de Diego et al study had limitation of low sample size and the study was a single-center study. Hence, our study will provide additional value to access the VA prevention role of ACEI/ARB and ARNI for HF patients receiving ICD or CRT-D.

A more recent retrospective study had studied the VA prevalence in relation to ARNI initiation in 151 patients who received ACEI or ARB in a single tertiary HF clinic in Belgium. Significant reductions were observed in ventricular tachycardia/fibrillation (VT/VF), occurrence of appropriate therapy, NSVT, and PVC. Improvement was observed in anti-tachycardia pacing (ATP) in patients with <90% ATP at baseline. The study found out that VA events reduction might be related to left ventricular reverse remodeling (Martens et al 2019). However, this study did not have measurements on N-Terminal prohormone of Brain Natriuretic Peptide (NT-proBNP).

To the best of our knowledge, there is a lack of understanding of the relationship between treatment (ACEI/ARB and ARNI) and VA in HFrEF patients with ICD or CRT-D in China.

1.2 Purpose

The purpose of this study is to generate effectiveness data of ARNI, in the Chinese HFrEF patients with implanted ICD or CRT-D.

2 Objectives and endpoints

This study aims to explore the effect of ARNI on VA and ICD or CRT-D shocks and ATP. The objectives and related endpoints are further described in Table 2-1.

Table 2-1 Objectives and related endpoints

Objectives	Endpoints			
Primary Objective	Endpoint for primary objective			
To assess the proportion of patients with VA events over 6 months of ACEI/ARB and 6 months of ARNI treatment	Proportion of patients with VA events over 6 months of ACEI/ARB and 6 months of ARNI treatment (VA events are defined as SVT, NSVT and PVC, ICD shock and ATP, the definitions of SVT, NSVT, PVC, ATP are as below)			

Ok	pjectives	Endpoints			
Se	condary Objectives	Endpoints for secondary objectives			
•	To assess the number of occurrences of VA events and ICD or CRT-D shocks over 6 months of ACEI/ARB and 6 months of ARNI treatment	Numbers of NSVT, SVT, PVC, ICD shock and ATP experienced by patients over 6 months of ACEI/ARB and 6 months of ARNI treatment			
•	To compare the changes in LVEF and NYHA level between ACEI/ARB and ARNI treatments	 LVEF (%) over 6 months of ACEI/ARB and 6 months of ARNI treatment NYHA level over 6 months of ACEI/ARB and 6 months of ARNI treatment 			
•	To compare the changes in the NT-proBNP level between ACEI/ARB and ARNI treatments	NT-proBNP (pg/mL) level over 6 months of ACEI/ARB and 6 months of ARNI treatment			
•	To compare the healthcare resource utilization of HF patients during ACEI/ARB and ARNI treatments	Number of hospitalizations for arrhythmia or HF related hospitalizations over 6 months of ACEI/ARB and 6 months of ARNI treatment			

Abbreviations: ACEI = angiotensin-converting enzyme inhibitor;

; ARB = angiotensin receptor blockers; ARNI = angiotensin receptor neprilysin inhibitor; ATP = anti-tachycardia pacing; CRT-D = cardiac resynchronization therapy-defibrillator; HF = heart failure; ICD = implantable cardioverter defibrillator; LVEF = left ventricular ejection fraction; NSVT = non-sustained ventricular tachycardia; NT-proBNP = N-Terminal prohormone of Brain Natriuretic Peptide; NYHA = New York Heart Association; PVC = premature ventricular contraction; SVT = sustained ventricular tachycardia; VA = ventricular arrhythmias

Note

Sustained ventricular tachycardia is defined as tachycardia with hemodynamic disorder or lasting for >30 seconds

Non-sustained ventricular tachycardia is defined by different ICD devices.

Premature ventricular contraction is defined as an early ventricular depolarization as determined by the device.

Anti-tachycardia pacing is defined as a low-energy alternative to high-energy biphasic shocks

2.1 Primary estimands

The primary clinical question of interest is: What is the effect of the ARNI versus ACEI/ARB on change on VA and ICD or CRT-D shocks and ATP in patients with implanted ICD or CRT-D?

The justification for the primary estimand is that it will capture both the effect of the study drug and the effect of additional medications, mirroring the conditions in clinical practice. Further details can be found in Section 12.

The primary estimand is described by the following attributes:

- 1. Population: patients defined through appropriate inclusion/exclusion criteria to reflect the targeted patient population for approval. Further details about the population are provided in Section 5.
- 2. Variable: VA, ICD and ATP events over 6 months of ACEI/ARB and 6 months of ARNI treatment.
- 3. Treatment of interest: ACEI/ARB for 6 months and ARNI for 6 months. Further details about the investigational treatment and control treatment are provided in Section 6.

Handling of remaining intercurrent events:

- 1. Treatment discontinuations for any reason: ignore (treatment policy strategy).
- 2. Unforeseen change in the dose of allowed concomitant medications: ignore (treatment policy strategy).
- 3. Unforeseen change in the dose of the investigational treatment or the control treatment due to adverse event or other reason: ignore (treatment policy strategy).

The summary measure: Proportion of patients with VA, ICD and ATP events over 6 months of ACEI/ARB and 6 months of ARNI treatment

[figure not shown]
2.2 Secondary estimands

None.

3 Study design

This will be a multicenter, interventional, open-label, and prospective single-arm study to evaluate the effect of ARNI on VAs in approximately 219 HFrEF patients receiving ICD or CRT-D in China (Figure 3-1).

Figure 3-1 Study design

Abbreviations: ACEI = Angiotensin-converting enzyme inhibitor; ARB = Angiotensin receptor blockers; ARNI = Angiotensin receptor neprilysin inhibitor; EOS = End of Study Note:

- *Data collection at Baseline(0), Month 1, Month 3, Month 6, Month 7, Month 9, and Month 12 according to the evaluation schedule.
- Dosage and titration plan of ACEI/ARB and ARNI treatments will be according to investigator's discretion and product label (Please refer to Table 6-2 and Table 6-3).
- 36-hr washout period is not needed for patients using ARB.

Page 23 of 63 Protocol No. CLCZ696BCN04

Patients will be informed about the study purpose and asked to sign an informed consent form. Demographics, etiology of HF, comorbidities, New York Heart Association (NYHA) class, baseline laboratory, electrocardiogram, echocardiogram, medical treatment, and implanted device (ICD or CRT-D) type and date will be collected at Baseline. Device data of patients will be collected for 12 months. Once the device is implanted, ACEI/ARB will be given to the patient. Dosage of ACEI/ARB will be based on investigator's discretion and up-titrated after 2-4 weeks to the maximum dosage the patients can tolerate and according to product label.

After 6 months, patients using ACEI need to undergo a 36-hr washout period (36-hr washout period is not needed for patients using ARB at month 6). Patients will then receive ARNI (sponsored by Novartis only for this study) while the dosage of ARNI will be according to investigator's discretion and up titrated to the maximum dosage the patient can tolerate or 200 mg bid as per guideline. The recommended starting dose of ARNI is presented in Table 6-3.

All patients will be followed up for 6 months for each treatment. After patients finalize the trial, the investigator will evaluate all patients and produce a report.

A Central Review Committee which composed by 2 separated subgroups. Subgroup 1 will be formed to confirm the type of events as defined by the device. If there are any discrepancies or disagreements in review, the Chairman will provide a final decision. The events that will be reviewed periodically include: appropriate shocks, inappropriate shocks, SVT, NSVT, PVC, ATP, Subgroup 2 will review SAE reports.

An Academic Committee composed by 11 members of certified electrophysiologists is formed to design and revise this study.

4 Rationale

4.1 Rationale for study design

The purpose of this study is to generate effectiveness data of ARNI, in the Chinese HFrEF patients with implanted ICD or CRT-D.

The rationale of this study is to compare the effect of ACEI/ARB with the effect of ARNI on VA events for HFrEF patients with ICD or CRT-D, thus a multicenter, interventional, openlabel, and prospective single-arm study was considered.

4.2 Rationale for dose/regimen and duration of treatment

The dosage of ARNI will be according to investigator's discretion and up titrate to the maximum dosage the patient can tolerate or 200 mg bid. In addition, 6-month is long enough to see the VA events changes after switch to ARNI.

Major clinical trials have established ACEI/ARB treatment as the standard of care for RAAS blockade and ACEI/ARB is recommended by treatment guidelines as the treatment of choice for HFrEF patients. ACEI/ARB has been shown to be superior to placebo in reducing mortality in HFrEF and is mostly used as comparator in large randomized controlled trials in HF.

4.3 Rationale for choice of control drugs (comparator) or combination drugs

ACEI/ARB are chosen as the comparator in this study. The ACEI/ARB treatment has been used as the standard of care for RAAS blockade and is recommended by treatment guidelines as the first-line treatment for HFrEF patients (Yancy et al 2017).

4.4 Rationale for public health emergency mitigation procedures

In the event of a public health emergency as declared by local or regional authorities (i.e., pandemic, epidemic or natural disaster), mitigation procedures may be required to ensure participant safety and trial integrity and are listed in relevant sections of the study protocol. Notification of the public health emergency should be discussed with Novartis prior to implementation of mitigation procedures, and permitted/approved by local or regional health authorities and ethics committees as appropriate.

4.5 Purpose and timing of interim analyses/design adaptations

The study will have one interim analysis (IA) and one final analysis (FA). The intent of the interim analysis is to stop for futility or high incidence of safety events and re-evaluate minimum sample size required. It is planned once at least 110 patients (half of the required sample size) have completed the study. All study endpoints stated in Section 2 will be analyzed.

4.6 Risks and benefits

Appropriate eligibility criteria and specific dose-limiting toxicity definitions, as well as specific dose modification and stopping rules, are included in this protocol.

The risk to patients in this trial may be minimized by compliance with the eligibility criteria and study procedures, as well as close clinical monitoring.

Women of child-bearing potential must be informed that taking the study treatment may cause injury and death to the fetus if pregnancy were to occur during the study, and agree that in order to participate in the study they must adhere to the contraception requirements. If there is any question that the patient will not reliably comply, they should not be entered in the study.

The overall benefit-risk balance of ARNI is positive for the treatment of HF (NYHA class II-IV) in patients with systolic dysfunction.

In the context of COVID-19 pandemic, there is still lack of evidence about the risks or benefits of ARNI and ACEI/ARB in COVID-19 patients.

5 Study Population

The study population will consist of approximately 219 patients with HFrEF (left ventricular ejection fraction [LVEF] ≤40%) in 25 sites, aged between 18 years and 80 years, receiving ICD/CRT-D devices.

5.1 Inclusion criteria

Participants eligible for inclusion in this study must meet all of the following criteria:

- 1. Male or female patients ≥ 18 and ≤ 80 years of age.
- 2. Implanted with an ICD or CRT-D within 2 weeks.
- 3. NYHA functional class II IV.
- 4. LVEF ≤40% (measured by echocardiography).
- 5. Signed informed consent must be obtained prior to participation in the study.

5.2 Exclusion criteria

Participants meeting any of the following criteria are not eligible for inclusion in this study.

- 1. History of hypersensitivity to any of the study treatments or its excipients or to drugs of similar chemical classes.
- 2. Patient received target dose (≥200 mg/d) of ARNI for 2 weeks continuously within the 6-week period prior to study enrollment.
- 3. Participation in other clinical studies 3 months prior to participating study.
- 4. Advanced cancer or other significant comorbidities with life expectancy of <1 year.
- 5. Previous history of angioedema associated with ACEI/ARB treatment, hereditary or idiopathic angioedema.
- 6. Patients with renal artery stenosis history.
- 7. Current stage D HF patients requiring vasoactive drugs.
- 8. Symptomatic hypotension < 100/60 mmHg at visit 1 (screening) or Symptomatic hypotension < 90/60 mmHg in anti-hypertension drug treatment at visit 1 (screening).
- 9. Serum potassium >5.4 mmol/L at visit 1 (screening).
- 10. Estimated glomerular filtration rate (eGFR) < 30 mL/min/1.73m² as measured at visit 1 (screening).
- 11. Pregnant or nursing (lactating) women.
- 12. Other exclusion depend on investigator's discretion.

6 Treatment

6.1 Study treatment

6.1.1 Investigational and control drugs

Investigational and control drugs are summarized in Table 6-1 (no limitation to the list).

Patients will receive ACEI/ARB, where generics are acceptable and listed in Table 6-1. Patients will initiate ARNI treatment after a 36-hr washout period after the ACEI treatment. Basically, initiated ARNI dosage accord to ACEI/ARB alternative dosage, but investigators have discretion to prescribe ARNI dosage.

Table 6-1 Investigational and control drug

(Name) Dosage Form Administration (local)	Drug (Name)	Pharmaceutical Dosage Form	Route of Administration	Supply Type	Sponsor (local)
---	----------------	-------------------------------	----------------------------	-------------	--------------------

Drug (Name)	Pharmaceutical Dosage Form	Route of Administration	Supply Type	Sponsor (local)
Sacubitril/Valsartan, 50mg	Tablet	Oral use	Oral use Open label subject packs;	
Control Drug				
ACEI				
Enalapril	Tablet	Oral use	Open label subject packs;	No supply
Captopril, 6.25 mg, 50 mg	Tablet	Oral use	Open label subject packs;	No supply
Perindopril, 2 mg, 8 mg	Tablet	Oral use	Open label subject packs;	No supply
Ramipril, 1.25 mg, 10 mg	Tablet	Oral use	Open label subject packs;	No supply
Benazepril, 2.5 mg, 20 mg	Tablet	Oral use	Open label subject packs;	No supply
ARB				
Candesartan, 4 mg, 32 mg	Tablet	Oral use	Open label subject packs;	No supply
Valsartan, 40 mg, 160 mg	Capsule	Oral use	Open label subject packs;	No supply
Losartan, 25 mg, 150 mg	Tablet	Oral use	Open label subject packs;	No supply

6.1.2 Additional study treatments

No other treatment beyond investigational drug and control drug are included in this trial.

6.1.3 Supply of study treatment

ARNI drugs will be supplied in this study by Novartis. Open drug label should be attached on each pack before transport to every site. Every site is responsible for drug storage, drug dispense, drug recycle and recording by documents.

6.1.4 Treatment arms/group

This is a single-arm study.

6.1.5 Treatment duration

The planned duration of treatment for ACEI/ARB and ARNI is 6 months each. During the ACEI/ARB period, the drug choice and dosage are at the discretion of the physician. The EOS will occur when the pre-specified number of patients completed the 12 months treatment. Patients may be discontinued earlier due to unacceptable toxicity and/or treatment is discontinued at the discretion of the investigator or the patient. For patients who in the opinion of the investigator are still deriving clinical benefit from ARNI, every effort will be made to continue provision of study treatment.

6.2 Other treatments

6.2.1 Concomitant therapy

All medications, procedures, and significant non-drug therapies (including physical therapy and blood transfusions) administered after the patient was enrolled into the study must be recorded on the appropriate electronic Case Report Forms (eCRF).

Each concomitant drug must be individually assessed against all exclusion criteria and prohibited medication. If in doubt, the Investigator should contact the Novartis medical monitor before allowing a new medication to be started. If the patient is already enrolled, contact Novartis to determine if the patient should continue participation in the study.

The concomitant use of other ACEIs or ARBs is strictly prohibited while the patient is receiving ARNI. Study medication should be stopped the day prior to addition of other ACEIs or ARBs.

Drugs for arrhythmia include antiarrhythmic drugs (amiodarone), beta-2 blockers (metoprolol sustained release tablets), and digitalis drugs (digoxin). Except for titration dose adjustment of beta-2 beta blockers, no special dose adjustment for other drugs. Amiodarone dosage must be consistent for patient treatment during this study, if radiofrequency ablation is necessary, the patient should withdraw from the study.

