6.2.2 Prohibited medication

Followed by ARNI instructive document. Concomitant use of ARNI with an ACEI/ARB is contraindicated because of the increased risk of angioedema.

Bile acid sequestrants (cholestyramine and colestipol) are also prohibited to avoid disturbing effect on the drug absorption of study medication.

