6.2.3 Rescue medication

There is no rescue medication, however in the event of hyperkalemia, investigator should review the medical regimen (including dietary supplements and over-the-counter medications) for agents known to cause hyperkalemia. Any patient who experiences a potassium level > 6.0 mmol/L confirmed by repeated same blood sample testing may be discontinued from the study treatment.

If symptomatic hypotension occurs, correct any treatable cause. If hypotension persists, any anti-hypertensive drug and non-disease-modifying drugs, such as diuretics, calcium channel blockers, nitrates, and α -blockers, should be down-titrated or stopped. If hypotension persists, the study drug should be temporarily withdrawn, the re-initiation of ARNI will be at Investigator discretion. ARNI is unlikely to be removed by hemodialysis because of high protein binding.

If ICD electrical storm occurs, correct the underlying arrhythmia. Differential diagnosis to the arrhythmia should be determined, with patient hospitalized and observed by an electrophysiologist. Drugs such as amiodarone and anti-arrhythmic agents can be used.

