6.8.3 Instruction for prescribing and taking study treatment

The study drug dosage will be under investigator's discretion according to local guideline and product label (Table 6-2). Patients should take their morning study dose at approximately 08:00 (8 AM) and their evening study dose at approximately 19:00 (7 PM). The study medication should be taken with a glass of water with or without food. If the patient misses taking any study drug dose, he/she should take it as soon as possible, unless if it is almost time for the following scheduled dose. In this case, the patient should skip the missed dose and take the regular study drug administration schedule.

All dosages prescribed and dispensed to the patients and all dose changes during the study must be recorded in the Dosage Administration Record eCRF.

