9.1 Discontinuation and completion

9.1.1 Study treatment discontinuation and study discontinuation

Discontinuation of study treatment for a patient occurs when study treatment is stopped earlier than the protocol planned duration, and can be initiated by either the patient or the investigator.

The investigator must discontinue study treatment for a given patient if, he/she believes that continuation would negatively impact the patient's well-being.

Discontinuation from study treatment is required under the following circumstances:

- 1. Patient/guardian decision
- 2. Pregnancy
- 3. Use of prohibited treatment as per recommendations in the prohibited treatment section
- 4. ACEI/ARBs daily dosage below guided dosage last for 1 month
- 5. Any situation in which study participation might result in a safety risk to the patient
- 6. Withdrawal of informed consent

Study treatment may be discontinued at the investigator's discretion if any of the following occurs:

- 1. Any severe, or suspected AE, that may jeopardize patient well-being, if the study drug is continued
- 2. Suspected occurrence of angioedema
- 3. Serum potassium >6.0 mmol/L at follow Visit
- 4. Any laboratory abnormalities that in the judgment of the investigator, taking into consideration the patient's overall status, prevents the patient from continuing participation in the study

If discontinuation of study treatment occurs, the Investigator should make a reasonable effort to understand the primary reason for the patient's premature discontinuation of study treatment and record this information.

Patients who discontinue study treatment or who decide they do not wish to participate in the study further should NOT be considered withdrawn from the study UNLESS they withdraw their consent (see withdraw of informed consent section). Where possible, they should return for the assessments indicated in the assessment schedule. If they fail to return for these assessments for unknown reasons, every effort (e.g. telephone, email, letter) should be made to contact the patient/pre-designated contact as specified in the lost to follow-up section. This contact should preferably be done according to the study visit schedule. Patients are to be discontinued from the study treatment if patient has not received the study treatment for > 14 days.

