9.3 Study completion and post-study treatment

Study completion is defined as when the last patient finishes their Study Completion visit and any repeat assessments associated with this visit have been documented and followed-up appropriately by the Investigator or, in the event of an early study termination decision, the date of that decision (e.g. Each patient will be required to complete the study in its entirety and thereafter no further study treatment will be made available to them).

All treated patients should have a safety follow-up call conducted 30 days after last administration of study treatment. The information collected is kept as source documentation. All SAEs reported during this time period must be reported as described in Section 10.1.3. Documentation of attempts to contact the patient should be recorded in the source documentation.

Continuing care should be provided by the investigator and/or referring physician based on patient availability for follow-up. This care may include:

Enrollment in an extension study, if any

10 Safety monitoring and reporting

The definitions of adverse events (AEs) and serious adverse events (SAEs) can be found in Section 10.1.

The Investigator and any qualified designees are responsible for detecting, documenting, and recording events that meet the definition of an AE or SAE and remain responsible for following up.

The method of recording, evaluating, and assessing causality of AEs and SAEs and the procedures for completing and transmitting SAE reports are provided in Section 10.1.3.

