12.4 Analysis of the primary endpoint

The purpose of primary objectives are to explore the effect of ARNI and ACEI/ARB in HFrEF patients with ICD or CRT-D in terms of VA events and in terms of ICD shocks and ATP using primary estimand described in Section 2.1.

In this study, patients will be observed for 6 months under ACEI/ARB alone. Then, ARNI treatment will be initiated (ACEI/ARB stopped, 36-hr washout period applied for patients using ACEI only) and patients will be observed for another 6 months under ARNI.

Multiple primary endpoints will be evaluated in this study during 2 different treatment periods, that are 6 months of ACEI/ARB treatment and 6 months of ARNI treatment (see detailed definitions in Section 12.4.1.)

Since the endpoints are all paired qualitative variable, McNemar Test will be used respectively to assess the difference in primary endpoint proportion between treatments.

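### Protocol 6.2.1 sets the gap between stopping ARNI and starting an ACEI in days, not hours, and so allows a start 13 hours after the last ARNI dose on the study-dose clock

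*Protocol*

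**What the plan says.** Protocol 6.2.1 bars other ACEIs and ARBs while a patient is on ARNI, and then gives the rule for adding one: "Study medication should be stopped the day prior to addition of other ACEIs or ARBs". No other sentence in the protocol or SAP sets a gap in this direction.

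In the other direction the interval is in hours. Protocol 6.1.1 says "Patients will initiate ARNI treatment after a 36-hr washout period after the ACEI treatment", and 12.4 limits its scope: "36-hr washout period applied for patients using ACEI only". The protocol summary, protocol section 3 and SAP section 3 say the same. All of these statements concern the month 6 switch from ACEI to ARNI.

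Protocol 6.2.2 gives the safety reason without limiting it to one order of administration: "Concomitant use of ARNI with an ACEI/ARB is contraindicated because of the increased risk of angioedema". The same section defers to an ARNI instructive document that is not supplied and quotes no interval from it.

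ARNI is taken twice daily (Table 6-2). Section 6.8.3 puts study doses at approximately 08:00 and 19:00.

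**The concern.** A rule stated as the preceding day has two ordinary readings. On the short reading, the patient takes ARNI on that day and starts the ACEI on the next. On the long reading, the patient takes no ARNI on that day. The two can differ by a full day, for a drug pair that the protocol itself contraindicates.

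The rule can come into use when ARNI is stopped for good under 9.1.1, for example for "Any severe, or suspected AE, that may jeopardize patient well-being, if the study drug is continued". Such patients stay in the study unless they withdraw consent, and their new treatments continue to be recorded. Section 4.3 describes ACEI/ARB as first-line in HFrEF, so a return to an ACEI is foreseeable. The same question arises at completion, because 9.3 says that "thereafter no further study treatment will be made available to them". However, 6.1.5 foresees continued supply for patients who still benefit, so not every completer would switch.

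What is at stake is patient safety, specifically angioedema. The protocol treats that risk seriously elsewhere: 5.2 excludes patients with such a history, and 9.1.1 lists suspected angioedema as a reason to stop treatment.

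**Working it through.** The plan states no ARNI-to-ACEI gap in hours, so there is no figure to reproduce. The check is clock subtraction.

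**Inputs**
- Dose times: about 08:00 and 19:00 (protocol 6.8.3).
- ARNI twice daily (Table 6-2).
- Comparison value: 36 h, which the protocol states only for ACEI to ARNI (6.1.1, 12.4).
- Assumption: the first ACEI dose also falls at 08:00 or 19:00. Section 6.8.3 gives these times for study doses, and only approximately. The assumption is relaxed below.

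**Formula.** Call the day of the first ACEI dose day 0. Gap = time of first ACEI dose − time of last ARNI dose.

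**ACEI at 08:00 or 19:00 on day 0**

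| Last ARNI dose | ACEI at 08:00 | ACEI at 19:00 |
|---|---|---|
| 19:00, day −1 | 13 h | 24 h |
| 08:00, day −1 | 24 h | 35 h |
| 19:00, day −2 | 37 h | 48 h |
| 08:00, day −2 | 48 h | 59 h |

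If ARNI is taken on the day before, the range is 13 to 35 h. Against 36 h the shortfalls are 36 − 13 = 23, 36 − 24 = 12 (twice) and 36 − 35 = 1 h. If ARNI is not taken on the day before, the range is 37 to 59 h and there is no shortfall.

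**ACEI at any hour of day 0 (00:00 to 24:00)**

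| Last ARNI dose | Gap | 36 h reached on day 0 at |
|---|---|---|
| 19:00, day −1 | 5 to 29 h | not reached |
| 08:00, day −1 | 16 to 40 h | 20:00 |
| 19:00, day −2 | 29 to 53 h | 07:00 |
| 08:00, day −2 | 40 to 64 h | always met |

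The short reading then gives about 5 to 40 h and the long reading 29 h or more. Neither lies wholly on one side of 36 h, so the lack of stated hours matters under both.

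**Extra delay under a 36 h minimum.** Move the ACEI to the first 08:00 or 19:00 slot at or after 36 h.
- Last ARNI dose at 19:00 on day −1: the new slot is at 37 h, so the delay is 37 − 13 = 24 h or 37 − 24 = 13 h.
- Last ARNI dose at 08:00 on day −1: the new slot is at 48 h, so the delay is 48 − 24 = 24 h or 48 − 35 = 13 h.

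**The case against.** The strongest objection is that the 36 h benchmark is borrowed. Every 36 h statement in the documents concerns ACEI to ARNI. A reader might infer that 6.2.1 breaches the protocol's own washout, but the documents do not support that, because they set no such interval after ARNI. This stands. What remains without the benchmark is that a rule for a contraindicated pair has no hours attached and allows a gap of 13 h.

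The label may already supply the interval. Section 6.2.2 defers to the instructive document, 6.5 and 6.5.3 tie interruptions and dose changes to the product label, and 6.2.1 sends doubtful cases to the medical monitor. This stands in part: those sources cannot be seen here and may settle the matter. But general deference does not displace an explicit rule, and a site that reads the rule as allowing an evening tablet followed by an ACEI the next morning may see no doubt to raise.

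A reader might also infer that one reading always clears 36 h and the other never does. That holds only on the 08:00/19:00 clock.

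Nor is withdrawal for low blood pressure a good example of when the rule would be used. Section 6.2.3 says "If hypotension persists, the study drug should be temporarily withdrawn, the re-initiation of ARNI will be at Investigator discretion", so the step it foresees is a return to ARNI, not an ACEI. Finally, 6.2.1 governs concomitant therapy during the study, and 9.3 leaves later care to the investigator or referring physician. Applying the rule to the end-of-study switch would be an extension for the sponsor to decide.

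**Conclusion.** The point holds as a safety wording gap that is cheap to close. Section 6.2.1 leaves the ARNI-to-ACEI interval open to two readings: 13 to 35 h against 37 h or more on the study-dose clock, or about 5 to 40 h against 29 h or more with the ACEI at any hour. The shortest clock case, an ACEI on the morning after the last evening ARNI dose, is an ordinary sequence for a twice-daily drug.

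The conclusion that the rule is imprecise rests on the text alone. The conclusion that the short reading is too short rests on carrying 36 h over to the reverse order, which needs confirmation from the label. The rule matters mainly for permanent stops under 9.1.1 and, if the sponsor extends it there, for the switch at completion.

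The documents do not say how many patients would move from ARNI to an ACEI, so no number at risk is claimed. Nothing is claimed about ARBs. The efficacy analysis, power and error rate do not change.

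**What to change.** Keep the day-prior rule for ARBs. Add to 6.2.1: *An ACEI must not be started until at least 36 hours after the last ARNI dose.* Before release, the medical team should check the figure against the ARNI label and use the label's figure if it differs. State that the sentence applies when treatment is stopped early under 9.1.1, and decide whether to extend it to the end-of-study switch in 9.3.

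The cost is one sentence in a written amendment, with approval by the sponsor, the IRB/IEC and, where required, the health authorities (14.1), plus a site memo. No visits or procedures are added. The clinical cost is about 13 or 24 more hours without RAAS blockade for a patient moving to an ACEI who would have followed the short reading. Patients moving to an ARB see no change.
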